10.1.2 Clinical Events Committee (CEC)

The Clinical Events Committee (CEC) is an independent committee that will provide a standard, systematic and unbiased assessment of pre-determined endpoints to ensure that they are adjudicated uniformly by a single group, using the definitions specified in the Protocol and CEC Charter.

The CEC will consist of a minimum of three members and will be comprised of physicians with expertise in CV surgery, interventional cardiology, heart failure, and neurology.

The scope, procedures, and events classification system will be defined in a written CEC charter.

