	
2) Duration of symptoms:
 
• A focal or global neurological deficit \geq 24 hours• A focal or global neurological deficit $<$ 24 hours if available neuroimaging indicates a new intracranial or subarachnoid hemorrhage (hemorrhagic stroke) or central nervous system infarction (ischemic stroke)• The neurological deficit results in death 
3) No other readily identifiable non-stroke cause for the clinical presentation (e.g. brain tumor, trauma, infection, hypoglycemia, peripheral lesion, pharmacological influences) to be determined by or in conjunction with designated neurologist.*
 
4) Confirmation of the diagnosis by at least one of the following:
 
• Neurologist or neurosurgical specialist, or• Neuroimaging procedure (CT scan or brain MRI)• Non-neurologist physician (if neurologist is not available)• Clinical presentation alone 
Stroke types will be classified as:
 
• Ischemic: an acute symptomatic episode of focal cerebral, spinal, or retinal dysfunction caused by an infarction of the central nervous system tissue• Hemorrhagic: an acute episode of focal or global cerebral or spinal dysfunction caused by intraparenchymal, intraventricular, or subarachnoid hemorrhage• Undetermined: if there is insufficient information to allow categorization as ischemic or hemorrhagic 
TIA Acute episode of a focal or global neurological deficit fulfilling the following criteria:
 
1) Resulting in at least one of the following:
 
• Change in level of consciousness• Hemiplegia• Hemiparesis• Numbness• Sensory loss affecting one side of the body• Dysphasia or aphasia• Hemianopia• Amaurosis fugax• Other neurological signs or symptoms consistent with stroke
--	--

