	
2) Duration of deficit could be one of the following:
 
 • A focal or global neurological deficit < 24 hours • Any available neuroimaging does not demonstrate a new hemorrhage or infarct 
3) No other readily identifiable non-stroke cause for the clinical presentation (e.g. brain tumor, trauma, infection, hypoglycemia, peripheral lesion, pharmacological influences) to be determined by or in conjunction with designated neurologist.*
 
Notes: *Patients with non-focal global encephalopathy will not be reported as a stroke without unequivocal evidence based upon neuroimaging studies. #If a stroke is reported without evidence of confirmation of the diagnosis by one of these methods, the event may still be considered a stroke on the basis of the clinical presentation alone.

Tricuspid Regurgitation	Tricuspid Regurgitation (TR), tricuspid insufficiency or tricuspid incompetence describes a condition in which blood flow through the tricuspid valve flows in the incorrect direction during part of the cardiac cycle.
Unanticipated Adverse Device Effect (UADE) 21 CFR part 812.3 (s)	Serious adverse effect on health or safety or any life-threatening problem or death caused by, or associated with, a device, if that effect, problem, or death was not previously identified in nature, severity, or degree of incidence in the investigational plan or application (including a supplementary plan or application), or any other unanticipated serious problem associated with a device that relates to the rights, safety, or welfare of subjects.
Unanticipated Serious Adverse Device Effect (USADE)	Serious adverse device effect which by its nature, incidence, severity or outcome has not been identified in the current version of the risk analysis report NOTE Anticipated serious adverse device effect (ASADE) is an effect which by its nature, incidence, severity or outcome has been identified in the risk analysis report.

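### The TIA definition takes short duration and negative imaging as alternatives, so it also admits events that meet the stroke definition, and the Protocol and SAP give no rule that stroke takes precedence

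*Protocol*

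**What the plan says.** The entry for stroke and TIA in Protocol Section 17 sets out two parallel lists.

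- **Stroke, criterion 2**, under the label "Duration of symptoms", has three options. The first is a deficit of 24 hours or more, with no imaging condition. The second is a shorter deficit for which imaging shows new bleeding or infarction. The third is "The neurological deficit results in death". No connector is printed, but the options only make sense as alternatives.
- **Stroke, criterion 4** (confirmation) can be met by "Clinical presentation alone".
- **TIA, criterion 2** opens with "Duration of deficit could be one of the following". Its first item is a deficit under 24 hours, with no imaging condition. Its second is "Any available neuroimaging does not demonstrate a new hemorrhage or infarct", with no time limit.

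The symptom list and the requirement of no other evident cause are the same in both entries.

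Stroke is a component of the primary safety composite (Protocol 7.5, SAP 3.1) and TIA is not. Clinical success requires freedom from MAE at 30 days (Protocol 7.5), and FDA device success requires freedom from stroke (SAP 6.6). Protocol 10.1.2 has the Clinical Events Committee (CEC) adjudicate "using the definitions specified in the Protocol and CEC Charter". The SAP adds no definition of stroke or TIA.

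**The concern.** A TIA category should hold the events that fall short of stroke. With its two conditions offered as alternatives, this one does not. A six-hour aphasia with a new infarct on MRI qualifies by duration, and a 30-hour hemiparesis with a negative CT qualifies by imaging. Both also satisfy stroke criterion 2. The imaging item sits under a line about duration, which suggests a drafting slip.

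At the least, a TIA count made from this definition contains strokes. More is at stake if adjudication gives each event a single label. Only the stroke label feeds the primary safety endpoint, the later MAE endpoints, clinical success and FDA device success, so a choice of TIA for an overlapping event can move these results only in the favourable direction. The label also drives data collection, because the modified Rankin Scale at follow-up is tied to having had a stroke (Protocol 7.8.7.8).

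**Working it through.** The plan states no figure to reproduce, so the check is one of logic, followed by the size of one changed label.

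**Step 1: which criterion can separate the two entries.** Stroke criteria 1 and 3 are repeated in the TIA entry, and stroke criterion 4 can be met on clinical grounds. Only criterion 2 is left to distinguish them. One note under the entry narrows this: non-focal global encephalopathy is not reported as stroke without clear imaging evidence. The overlap at 24 hours or more with negative imaging therefore concerns other deficits.

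**Step 2: non-fatal events, criterion 2 only.**

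| Duration | Imaging | Stroke | TIA as written (either) | TIA if both required |
|---|---|---|---|---|
| < 24 h | new lesion | yes | **yes** | no |
| < 24 h | negative | no | yes | yes |
| < 24 h | none done | no | yes | yes* |
| ≥ 24 h | new lesion | yes | no | no |
| ≥ 24 h | negative | yes | **yes** | no |
| ≥ 24 h | none done | yes | **on one reading*** | no |

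*If the imaging condition is taken as satisfied when no imaging exists.

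As written, 2 of 6 combinations certainly meet both entries, and 3 of 6 do on the reading marked with the asterisk. With both TIA conditions required, none does: 4 are stroke only and 2 are TIA only.

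**Step 3: fatal events.** If the deficit results in death, all 6 combinations are strokes. As written, 4 of the 6 also meet the TIA entry (5 on the same reading). With both conditions required, 2 still do: under 24 hours with negative imaging, and under 24 hours with none. Joining the conditions is therefore not sufficient without a precedence rule. For the MAE composite these fatal cases matter less, because Section 17 counts any death not unequivocally non-cardiovascular as cardiovascular, and cardiovascular death is itself an MAE component.

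**Step 4: size of one changed label.** For a patient with no other MAE, the change in the MAE proportion is 1/n.

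- Primary cohort, n = 60 (Protocol 7.1): 1/60 = 1.67 percentage points.
- First analysis, n = 30 (Protocol 9.3): 1/30 = 3.33 percentage points.

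Illustration with assumed counts and exact (Clopper-Pearson) 95% limits: 2/60 = 3.3% (0.4 to 11.5) against 3/60 = 5.0% (1.0 to 13.9). SAP 6.3 plans Kaplan-Meier for MAE, and SAP 4 makes the per-protocol population primary. These figures therefore approximate the planned estimate when follow-up to 30 days is nearly complete and few patients are dropped for major deviations.

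**The case against.** The strongest reply is that the primary endpoint counts strokes and the stroke entry stands on its own. It contains no clause excluding events that also qualify as TIA, and nothing in either document lets a TIA label cancel a stroke. An adjudicator who applies the stroke entry to either example arrives at stroke, and so at an MAE. This stands. A reader might infer that two adjudicators who both follow the Protocol could place the same event inside or outside the primary endpoint, or that the plan builds in an undercount of strokes. The documents do not support that, because it needs the further premise that the labels are exclusive and that TIA may be chosen.

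Other replies also carry weight:

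- The classification system is left to the CEC charter (Protocol 10.1.2, SAP 7.7), which was not available and may settle precedence.
- Adjudication is by a single independent group that includes neurology expertise, and the notes allow stroke on the clinical picture alone. Both lean towards stroke.
- It would be tempting to say that the imaging item is met automatically when no imaging was done. That is only one reading.
- The entry is attributed to a consensus document. Whether its wording follows that source cannot be checked here.

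None of this removes the overlap. The TIA criterion admits strokes on its face, and neither document supplied states which label prevails.

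**Conclusion.** TIA criterion 2 is wrong as written. The certain consequence is limited: any TIA tabulation that follows it will include events that are strokes. An effect on the primary safety endpoint is conditional. It arises only if each event gets one label, TIA is chosen for an overlapping event, and the CEC charter does not forbid that choice. The stroke and MAE rates would then be too low, and clinical success and FDA device success too high, by about 1.7 points for each patient affected if n = 60 and 3.3 points at the 30-patient analysis. This assumes that the patient has no other MAE and, for the success endpoints, no other reason to fail them.

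The documents give no stroke or TIA rate, so the number of such patients cannot be estimated. MAE has no hypothesis test or performance goal, so no formal decision turns on it. It remains the primary safety result of a study meant to inform later designs, and with 60 patients a single label is visible in the rate.

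**What to change.** Make two changes in Protocol Section 17 and confirm both in the CEC charter.

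1. Add a precedence rule: *an event meeting the stroke criteria, including a deficit resulting in death, is classified as stroke and not as TIA.* This is the essential part, since it resolves every overlapping combination, fatal ones included.
2. Join the two TIA conditions by *and*: a deficit under 24 hours, and no new hemorrhage or infarct on any imaging obtained. Say expressly that the second condition is taken as met when no imaging was obtained. Otherwise a short, non-fatal deficit without imaging could fall into neither category.

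Then re-read any event already adjudicated as TIA against the stroke criteria.

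The text is short, but a Protocol change needs a written amendment agreed with the regulator and the ethics committees (Protocol Section 14). If the charter already contains the precedence rule, or can be clarified sooner, that protects adjudication in the meantime. The possible downside for the sponsor is a slightly higher stroke rate.

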18 CHRONIC MR SEVERITY GRADING BY ECHOCARDIOGRAPHY

This table is derived from the 2017 American Society of Echocardiography Native Valve Regurgitation Guidelines.

The only modification of note to the guidelines is the addition of a separate category for Trace MR. This category will be used to characterize regurgitation that is clinically insignificant and too little to quantify. In addition, the core lab overall has also subdivided the moderate MR category into mild-moderate and moderate-severe subcategories.

	Trace (0-1+)	Mild (1+)	Mild-Moderate (2+)	Moderate-Severe (3+)	Severe (4+)
Structural					
MV morphology	None or mild leaflet abnormality	None or mild leaflet abnormality	Moderate leaflet abnormality or moderate tenting	Moderate leaflet abnormality or moderate tenting	Severe valve lesions
LV and LA size	Usually normal	Usually normal	Normal or mild dilation	Normal or mild dilation	Dilated
Qualitative Doppler					
Color flow jet area	Small, central, narrow, brief	Small, central, narrow, brief	Variable	Variable	Large central jet (>50% of LA) or eccentric wall-impinging jet of variable size
Flow convergence	Not visible	Not visible, transient or small	Intermediate in size and duration	Intermediate in size and duration	Large throughout systole
CW Doppler jet	Faint	Faint/partial/parabolic	Dense but partial or parabolic	Dense but partial or parabolic	Holosystolic/dense/triangular
Semiquantitative					
Vena contracta width (cm)	< 0.3	< 0.3	Intermediate	Intermediate	≥ 0.7
Pulmonary vein flow	Systolic dominance	Systolic dominance	Normal or systolic blunting	Normal or systolic blunting	Minimal to no systolic flow / systolic flow reversal
Mitral inflow	A wave dominant	A wave dominant	Variable	Variable	E wave dominant (> 1.2 m/sec)
Quantitative					
EROA (cm ²)	< 0.2	< 0.2	0.20 – 0.29	0.30 – 0.39	≥ 0.40 (may be lower in secondary MR with elliptical EROA)
Regurg Vol (ml)	< 30	< 30	30 – 44	45 – 59	≥ 60 (may be lower in low flow conditions)
Regurg Fract (%)	< 30	< 30	30 – 39	40 – 49	≥ 50

Reference: Zoghbi et al. Recommendations for Noninvasive Evaluation of Native Valve Regurgitation. Journal of the American Society of Echocardiography. Volume 30, Number 4.

## GLOSSARY OF TERMS

Abbreviation	Definition
6MWT	Six-Minute Walk Test
AE	Adverse Event
CEC	Clinical Events Committee
CSR	Clinical Study Report
EF	Ejection Fraction
EFS	Early Feasibility Study
EOA	Effective Orifice Area
ITT	Intent-to-Treat
MAE	Major Adverse Event
MR	Mitral Regurgitation
NYHA	New York Heart Association
OUS	Outside of United States
SAP	Statistical Analysis Plan

## 1. INTRODUCTION

The statistical analysis plan (SAP) specifies the statistical methods to be implemented for the analysis of data collected within the scope of Edwards Lifesciences's Protocol with Study Number 2016-05, "The CLASP Study - Edwards PASCAL TrAnScatheter Mitral Valve RePair System Study", [REDACTED]

[REDACTED]

[REDACTED]

[REDACTED]

[REDACTED]

[REDACTED]

## 2. STUDY DESIGN

### 2.1. Study Objectives

The objectives of this clinical study are to:

- Evaluate the safety and performance of the Edwards PASCAL Transcatheter Mitral Valve Repair (TMVr) System
- Provide guidance for future clinical study designs utilizing the Edwards PASCAL System
- Provide guidance for future Edwards PASCAL System development efforts

### 2.2. Study Design

This is a multi-center (up to 20 sites), multi-national, prospective, single arm study. The analysis population will consist of 60 patients. No site will be allowed to enroll more than 20% of the analysis population. All enrolled study patients will be assessed for clinical follow-up at the following intervals: 30 days, 6 months, 1 year and annually for 5 years post implant procedure. In addition, the study allows for 0 to 3 roll-in patients per site where allowed, for a total maximum of 60 roll-in patients. The overall study therefore allows for up to 120 patients: 60 in the analysis population, and up to 60 additional roll-in patients.

Of the total enrollment, 45 patients will be enrolled in the U.S. at up to 9 clinical sites. In the event that the 60-patient analysis cohort fills prior to the completion of the US EFS cohort, the US EFS cohort may continue to enroll until completed.

### 3. STUDY ENDPOINTS

#### 3.1. Primary Endpoints

##### Safety:

Composite of major adverse events (MAE) defined as cardiovascular mortality, stroke, myocardial infarction, new need for renal replacement therapy, severe bleeding and re-intervention for study device related complications at 30 days.

##### Performance:

- Device success: device is deployed as intended and the delivery system is successfully retrieved as intended at the time of the patient's exit from the cardiac catheterization laboratory. Per device analysis.
- Procedural success: device success with evidence of MR reduction  $\leq$  MR2+ at discharge and without the need for a surgical or percutaneous intervention prior to hospital discharge. Per patient analysis.
- Clinical success: procedural success with evidence of MR reduction  $\leq$  MR2+ and without MAEs at 30 days. Per patient analysis.

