The ACCESS-EU was a prospective, multi-center, nonrandomized post-approval study conducted in 567 patients in Europe. In this patient population, the procedure was effective with low hospital mortality and low adverse event rates²⁴.

In these studies, it was observed that 30-day safety performance outcomes after MitraClip implantation are similar to those at one year. Only complications related to the underlying disease such as mortality and re-hospitalizations continually increase. Glower et al discussed "In these high-risk patients, the results of MV (mitral valve) device placement appear to be very stable from 30 days to 12 months". Additionally, Feldman et al²⁶ discussed: "The landmark analysis of this device demonstrated that the clinical failures primarily occurred within the first 6 months, most of which were caused by inadequate MR reduction during the index procedure or early SLDA (single-leaflet device attachment)."

Other recent commercially available (in select regions) Mitral Valve repair devices include percutaneous direct annuloplasty using Cardioband (Valtech Cardio, Israel, recently acquired by Edwards, Irvine, CA, USA; CE mark 2015), direct annuloplasty using Mitralign (Mitralign Inc., Tewksbury, MA; CE mark 2016), indirect annuloplasty using Carillon (Cardiac Dimensions, Kirkland, WA; CE mark 2009), and percutaneous chordal repair using NeoChord (NeoChord, Minneapolis, Minnesota; CE mark 2013).

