7.5 Primary Endpoints

Safety:

Composite of major adverse events (MAE) defined as cardiovascular mortality, stroke, myocardial infarction, new need for renal replacement therapy, severe bleeding and re-intervention for study device related complications at 30 days.

Performance:

- Device success: device is deployed as intended and the delivery system is successfully retrieved as intended at the time of the patient's exit from the cardiac catheterization laboratory. Per device analysis.
- Procedural success: device success with evidence of MR reduction \leq MR2+ at discharge and without the need for a surgical or percutaneous intervention prior to hospital discharge. Per patient analysis.
- Clinical success: procedural success with evidence of MR reduction \leq MR2+ and without MAEs at 30 days. Per patient analysis.

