Functional/ Secondary Mitral Regurgitation (M-VARC 2015)	Abnormal backflow of blood from left ventricle to left atrium principally caused by global or regional left ventricular remodeling and/or severe left atrial dilation. Severity is as defined by ASE.
Heart Team	Multidisciplinary team consisting of local experts experienced in the care of patients with mitral valve disease. At a minimum, the heart team should include a heart failure/valve cardiologist, an interventional cardiologist skilled in the relevant access and device implantation procedures, a mitral valve cardiac surgeon, and an imaging specialist.
Implant procedure (Index procedure)	The procedure in which placement of the investigational device in the mitral valve regurgitant orifice takes place
Infection	Known infection requiring intravenous antibiotics for other than prophylaxis, and/or extended hospitalization
KCCQ	Kansas City Cardiomyopathy Questionnaire is an instrument used to quantify physical function, symptoms, social function, self-efficacy and knowledge, and quality of life.
Major Adverse Events (MAE)	Cardiac mortality, stroke, myocardial infarction, new need for renal replacement therapy, severe bleeding, and non-elective cardiovascular surgery for device related complications.
Mitral regurgitation	The condition in which incompetency of the mitral valve causes abnormal backflow of blood from the left ventricle to the left atrium during the systolic phase of the cardiac cycle.

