#### 3.2. Secondary Endpoints and Clinical Outcomes

- Mitral regurgitation reduction at 30 days, 6 months, 1 year and annually thereafter over baseline
- All-cause mortality at 30 days, 6 months, 1 year, and annually thereafter
- Recurrent heart failure hospitalization at 30 days, 6 months, 1 year, and annually thereafter
- Re-intervention rates for mitral regurgitation at 30 days, 6 months, 1 year and annually thereafter
- Composite of major adverse events (MAE) defined as cardiovascular mortality, stroke, myocardial infarction, new need for renal replacement therapy, severe bleeding and re-intervention for study device related complications at 6 months, 1 year and annually thereafter
- Change in Left Ventricular End Diastolic Volume (LVEDV) at 6 months and 1 year and annually thereafter over baseline

- Change in Left Ventricular End Systolic Volume (LVESV) at 6 months and 1 year and annually thereafter over baseline
- Change in Pulmonary Artery Systolic Pressure at 6 months and 1 year and annually thereafter over baseline
- Change in 6MWT distance at 6 months and 1 year over baseline
- Change in Quality of Life (QoL) score, as measured by Kansas City Cardiomyopathy Questionnaire (KCCQ), and EQ5D at 30 days, 6 months and 1 year and annually thereafter over baseline
- Change in NYHA Functional Classification at 6 months and 1 year and annually thereafter over baseline
- Change in BNP/NT-pro-BNP level at 6 months and 1 year and annually thereafter over baseline
- Change in tricuspid regurgitation at 6 months and 1 year and annually thereafter over baseline
- Change in effective regurgitant orifice area (EROA) at 30 days, 6 months, 1 year and annually thereafter over baseline
- Change in mitral regurgitant volume at 30 days, 6 months and 1 year and yearly thereafter over baseline

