#### 6.6. Additional Analyses per FDA

Per FDA, the success rates based the following definitions will be summarized by counts and percentages.

FDA Device Success (30 day and all post-procedural intervals):

- Alive and stroke free, with
- Original intended device in place, and
- No additional surgical or interventional procedures related to access or the device since completion of the original procedure (i.e., exit from the cath lab/OR), and
- Intended performance of the device:
- Structural performance: No migration, embolization, detachment, fracture, hemolysis, thrombosis or endocarditis, etc., and
- Hemodynamic performance: Maintenance of relief of insufficiency without producing stenosis (stenosis = MV gradient > 5 mmHg; insufficiency = MR >2+), and
- Absence of para-device complications (e.g., leaflet, chordae or papillary muscle damage; LVOT gradient increase > 10 mmHg; hemodynamically significant ASD requiring closure)

FDA Procedural Success (30 day):

- Device success, and
- No device or procedure related SAE's (life threatening bleed; major vascular or cardiac structural complications requiring unplanned reintervention or surgery; stage 2 or 3 AKI (includes new dialysis); MI or need for PCI/CABG; severe HF or hypotension requiring IV inotrope, ultrafiltration or MCS; prolonged intubation > 48 hours)

FDA Technical Success (at exit from OR):

- Alive, with
- Successful access, delivery and retrieval of the device delivery system, and
- Deployment and correct positioning (including repositioning /recapture if needed) of the single intended device, and
- No need for additional unplanned or emergency surgery or re-intervention related to the device or access procedure

FDA Individual Patient Success (1 year):

FDA Device success and all of the following:

- No re-hospitalizations or re-interventions for the underlying condition (e.g., MR, HF)
- Return to prior living arrangement (or equivalent)
- Improvement vs. baseline in symptoms (e.g., NYHA Class improvement > 1 class)
- Improvement vs. baseline in functional status (e.g., 6MWT improvement > 25 meters)
- Improvement vs. baseline in QoL (e.g., KCCQ improvement > 10)

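### Between discharge and day 30, a repeat mitral procedure fails clinical success only if it is adjudicated a device related MAE, so some patients re-treated for MR can score as successes

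*SAP*

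**What the plan says.** SAP 3.1 and Protocol 7.5 define procedural success as device success with MR 2+ or less at discharge "and without the need for a surgical or percutaneous intervention prior to hospital discharge". Clinical success is procedural success plus MR 2+ or less "and without MAEs at 30 days. Per patient analysis". Protocol Section 17 repeats both definitions.

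The MAE composite in SAP 3.1 ends with "severe bleeding and re-intervention for study device related complications at 30 days"; Protocol 7.5 agrees. The MAE entry in Protocol Section 17 ends differently, with "severe bleeding, and non-elective cardiovascular surgery for device related complications". Section 17 also defines re-intervention as a procedure on the study device already in place or on the access site.

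A separate secondary endpoint covers "Re-intervention rates for mitral regurgitation at 30 days, 6 months, 1 year and annually thereafter" (SAP 3.2). It does not enter clinical success. Neither document says whether recurrent MR is a device related complication, or how to treat an MR grade taken after a second mitral procedure. SAP 6.3 summarizes clinical success by counts and percentages, with no hypothesis test or performance goal.

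**The concern.** The explicit bar on further intervention stops at discharge, while the endpoint is read at 30 days. In between, only the MAE component can turn a repeat mitral procedure into a failure, and that component depends on the reason for the procedure.

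An example: a patient is discharged at MR 2+, returns with MR 4+ around a stable implant, receives a second transcatheter device on day 14, and has MR 1+ on the 30-day echo. If the event is not adjudicated a device related complication and there is no other MAE, every part of clinical success is met. The MR grade that earns the success comes from the second procedure. Errors through this gap can only add successes.

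The protocol's background makes early failure a relevant question for this type of device. For the comparable clip it cites clinical failures mainly in the first 6 months, "most of which were caused by inadequate MR reduction during the index procedure or early SLDA".

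**Working it through.** The plan states no success rate, re-intervention rate, power or margin, so there is no figure to reproduce. The check is a trace of the definitions, followed by the arithmetic of one misclassified patient.

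**Trace.** Device success is assumed, with no intervention before discharge and no other MAE.

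| Path | MR at discharge | Event from discharge to day 30 | MR at 30 days | Clinical success |
|---|---|---|---|---|
| A | above 2+ | any | any | Failure (procedural success not met) |
| B | 2+ or less | none, or any | above 2+ | Failure (MR criterion) |
| C | 2+ or less | re-intervention adjudicated as device related | 2+ or less | Failure under SAP 3.1 and Protocol 7.5; under Section 17, failure only if it is non-elective cardiovascular surgery |
| D | 2+ or less | re-treatment for MR, not adjudicated as device related | 2+ or less | **Success** under either MAE wording |

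Path D is the gap. Path C becomes a second gap if the Section 17 wording governs, because a percutaneous or elective procedure then falls outside MAE. That is possible: under Protocol 10.1.2 the CEC adjudicates by the definitions in the Protocol and its charter, and the Protocol contains both wordings. A second device placed beside an untouched implant is also not clearly a re-intervention as Section 17 defines the term.

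The 30-day grade can be available in these patients. Even after explant, Protocol 7.8.7.11 keeps the patient in the study for another 30 days.

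**Size per patient.** The effect is 100/n points, with n from SAP 2.2, SAP 4 and Protocol 7.1, assuming all n are evaluable.

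- n = 60 (primary cohort): 100/60 = 1.67 points
- n = 30 (first analysis): 100/30 = 3.33 points
- n = 60 + 50 = 110 (pooled cohorts): 100/110 = 0.91 points

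**Illustration at n = 60.** The starting count of 54 and the number reclassified, k, are assumptions. Intervals are 95% Clopper-Pearson, the SAP 6.1 method.

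| k | Clinical success | 95% CI |
|---|---|---|
| 0 | 54/60 = 90.0% | 79.5 to 96.2 |
| 1 | 53/60 = 88.3% | 77.4 to 95.2 |
| 2 | 52/60 = 86.7% | 75.4 to 94.1 |
| 3 | 51/60 = 85.0% | 73.4 to 92.9 |

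**Frequency.** Let p be the proportion of patients re-treated for MR between discharge and day 30. The documents give no p, so the values below are assumptions. Treating every such patient as misclassified gives an upper bound: P(at least one) = 1 − (1 − p)^60, and the expected number is 60p.

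| Assumed p | P(at least one of 60) | Expected number |
|---|---|---|
| 1% | 1 − 0.99^60 = 45% | 0.6 |
| 2% | 1 − 0.98^60 = 70% | 1.2 |
| 3% | 1 − 0.97^60 = 84% | 1.8 |
| 5% | 1 − 0.95^60 = 95% | 3.0 |

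Only patients who meet every condition of path D (or of path C under Section 17) are misclassified, so the true numbers for a given p are lower.

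**The case against.** The strongest reply is that MAE may already catch most of these patients. Protocol 6.1 lists worsening mitral regurgitation, device migration including single-leaflet attachment, and implantation of a further transcatheter repair device among the possible complications of the system or procedure. The CEC could therefore class recurrent MR treated with a second device as a device related complication, and the CEC charter, which is not in these documents, may say so. Surgery could also produce an MAE through severe bleeding, which under Section 17 starts at the MVARC major level.

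This stands as a limit on size. It does not close the gap: a list of possible complications is not an adjudication rule, and listing MR re-intervention as its own endpoint suggests that it is a different event from the MAE component.

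Three stronger readings are tempting, and the documents do not support them.

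- **Every patient re-treated after discharge scores as a success.** Paths A, B and C show otherwise under the endpoint text.
- **FDA device success in SAP 6.6 plainly fails these patients and the primary endpoint does not.** The FDA clause reads "No additional surgical or interventional procedures related to access or the device since completion of the original procedure". It starts at exit from the procedure room, but it carries a device-or-access qualifier of its own, so it does not clearly catch path D either.
- **The cited experience with the comparable clip shows that the endpoint misses the main failure mode.** That statement concerns the first 6 months. Inadequate reduction that leaves MR above 2+ at discharge already fails, and single-leaflet attachment requiring intervention fits naturally under the MAE component of the endpoint text.

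It is also fair that no test or decision rule depends on clinical success, and that 30-day MR re-interventions are tabulated separately. Readers will see the events, but the separate table does not correct the primary percentage.

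**Conclusion.** The point holds in a limited form. A patient at MR 2+ or less at discharge, re-treated for MR by day 30, can be scored a clinical success on the re-treated valve if the procedure is not adjudicated a device related complication and no other MAE occurs. Under the Section 17 MAE wording, the same is true of device related re-interventions that are percutaneous or elective.

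The bias runs only towards success, at 1.7 points per affected patient at n=60 and 3.3 at n=30. How many patients are affected cannot be derived from the documents. One might infer that the trial's conclusions are invalid, but the analysis is descriptive, so no error rate or formal conclusion is at stake. Severity is moderate: a primary percentage that could be somewhat too high, for a reason that is easily removed.

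**What to change.** 1. In Protocol 7.5, Protocol Section 17 and SAP 3.1, add to clinical success: *and no surgical or percutaneous mitral valve re-intervention for any reason through day 30*. State that for this clause the term covers any further mitral valve procedure after the index procedure, whether or not it touches the implanted device, since the Section 17 definition is narrower.
2. State that an MR grade obtained after such a procedure does not count towards success. SAP 5.2 accepts the 30-day visit up to day 37, so this sentence should cover any mitral procedure done before the echo that is graded.
3. Reconcile the MAE entry in Protocol Section 17 with the composite in Protocol 7.5 and SAP 3.1, so that the CEC works from one definition.

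The cost is one clause and one sentence, plus the reconciliation. The re-intervention data are already collected for the secondary endpoint. The reported clinical success rate may be slightly lower, and a patient re-treated for a reason unrelated to the device would also count as a failure.
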